
Appendix 1

Eligibility Questionnaire

The next few questions are to confirm that you are eligible to participate in the study. After that we will ask you to provide some information about you, and answer some questions about your mood and your sleep. You can then complete the first relaxation exercise, so make sure you are somewhere comfortable and quiet and have some headphones.

How old are you?

16 (16) ... 25 (25)

Do you have access to a mobile/tablet or laptop, and headphones so that you can access the intervention?

No (1) Yes (2)

Do you use singing bowls music regularly (more than once a month)?

No (1) Yes (2)

Do you use guided meditation regularly (more than once a month)?

No (1) Yes (2)

Are you currently receiving treatment from a psychologist or psychiatrist?

No (1) Yes (2)

Appendix 2

Demographic questionnaire

Now we want to know a little bit about you... What gender do you most identify as?

Male (1)

Female (2)

Non-binary/third gender (3)

Prefer to self-describe: (4) _____

Prefer not to say (5)

Q4.3 What is your ethnicity? (Select all those that apply)

New Zealand European (1)

Maori (2)

Samoan (3)

Cook Island Maori (4)

Tongan (5)

Niuean (6)

Chinese (7)

Indian (8)

Other, such as Dutch, Japanese, Tokelauan (9)

Q4.4 What is your first language?

Q4.5 Please tell us a bit about your education

Still at secondary school (1)

Completed secondary school (2)

At University/Tec (3)

Completed University/Tec (4)

Q4.6 What qualifications have you completed? (tick all that apply)

Nil (1)

NCEA Level 1 or equivalent (2)

NCEA Level 2 or equivalent (3)

NCEA Level 3 or equivalent (4)

Trade - Specify (5) _____

Professional - Specify (6) _____

Tertiary - Specify (7) _____

Other - Specify (8) _____

Appendix 3

Abbreviated POMS (Revised Version)

Below is a list of words that describe feelings people have. Please **CIRCLE THE NUMBER THAT BEST DESCRIBES HOW YOU FEEL RIGHT NOW.**

		Not At All	A Little	Moderately	Quite a lot	Extremely
1	Tense	0	1	2	3	4
2	Angry	0	1	2	3	4
3	Worn Out	0	1	2	3	4
4	Unhappy	0	1	2	3	4
5	Proud	0	1	2	3	4
6	Lively	0	1	2	3	4
7	Confused	0	1	2	3	4
8	Sad	0	1	2	3	4
9	Active	0	1	2	3	4
10	On-edge	0	1	2	3	4
11	Grouchy	0	1	2	3	4
12	Ashamed	0	1	2	3	4
13	Energetic	0	1	2	3	4
14	Hopeless	0	1	2	3	4
15	Uneasy	0	1	2	3	4
16	Restless	0	1	2	3	4
17	Unable to concentrate	0	1	2	3	4
18	Fatigued	0	1	2	3	4
19	Competent	0	1	2	3	4
20	Annoyed	0	1	2	3	4
21	Discouraged	0	1	2	3	4
22	Resentful	0	1	2	3	4
23	Nervous	0	1	2	3	4
24	Miserable	0	1	2	3	4
25	Confident	0	1	2	3	4
26	Bitter	0	1	2	3	4
27	Exhausted	0	1	2	3	4
28	Anxious	0	1	2	3	4
29	Helpless	0	1	2	3	4
30	Weary	0	1	2	3	4
31	Satisfied	0	1	2	3	4
32	Bewildered	0	1	2	3	4
33	Furious	0	1	2	3	4
34	Full of pep	0	1	2	3	4
35	Worthless	0	1	2	3	4
36	Forgetful	0	1	2	3	4
37	Vigorous	0	1	2	3	4
38	Uncertain about things	0	1	2	3	4
39	Bushed	0	1	2	3	4
40	Embarrassed	0	1	2	3	4

Appendix 4

Auckland Sleep questionnaire (current sleep)

Please answer the following:

a. Do you have problems getting to sleep, staying asleep, poor quality sleep, or waking early such that it affects your functioning the next day – this includes feeling excessively sleepy the next day?

No Yes

b. Does this occur 3 or more times per week?

No Yes

c. Has it been like this for more than one week?

No Yes

d. How long have you had this problem? _____

e. If **yes**, was there some event that caused this? (Please describe.)

Were there specific reasons for your poor sleep? i.e. baby crying, sick family member, partying too late, work/school requirements? _____

f. Do you need medication to help your sleep, mood or stress?

Please tick one:

Not during the past month

Less than once a week

Once or twice a week

Three or more times a week

g. If **yes**, what is the name of this medicine(s) _____

h. During the past week, how would you rate your sleep quality overall?

Please tick one:

Very good

Fairly good

Fairly bad

Very bad

Last time point only

Do you have any feedback on the intervention? What did you think about it? Did you like it?

Would you recommend the intervention you experienced to other rangitahi?

Thank you for answering the questions. You've now completed the study. Over the next few days you will receive an email with links to the progressive muscle relaxation and singing bowls tracks so you can use them whenever you like

Appendix 5

Visual analogue scales

Overall, how do you feel right now? Move the slider along the line to indicate your response.

0 = Worst I have ever felt 100 = Best I have ever felt

0 10 20 30 40 50 60 70 80 90 100

Q1.3 How relaxed do you feel right now? Move the slider along the line to indicate your response.

0 = Not relaxed 100 = Very relaxed

0 10 20 30 40 50 60 70 80 90 100

Q1.4 How stressed do you feel right now? Move the slider along the line to indicate your response.

0 = Not stressed 100 = Very stressed

0 10 20 30 40 50 60 70 80 90 100

Appendix 6

Progressive Muscle Relaxation Script (Adapted from *The Anxiety & Phobia Workbook*, by Edmund J. Bourne)

Progressive muscle relaxation is an exercise that relaxes your mind and body by progressively tensing and relaxation muscle groups throughout your entire body. You will tense each muscle group vigorously, but without straining, and then suddenly release the tension and feel the muscle relax. You will tense each muscle for about 5 seconds. If you have any pain or discomfort at any of the targeted muscle groups feel free to omit that step. Throughout this exercise you may visualize the muscles tensing and a wave of relaxation flowing over them as you release that tension. It is important that you keep breathing throughout the exercise. Now let's begin....

Begin by finding a comfortable position either sitting or lying down in a location where you will not be interrupted.

Allow your attention to focus only on your body. If you begin to notice your mind wandering, bring it back to the muscle you are working on.

Take a deep breath through your abdomen, hold for a few second, and exhale slowly. Again, as you breathe notice your stomach rising and your lungs filling with air.

As you exhale, imagine the tension in your body being released and flowing out of your body.

And again inhale.....and exhale. Feel your body already relaxing.

As you go through each step, remember to keep breathing.

Now let's begin. Tighten the muscles in your forehead by raising your eyebrows as high as you can. Hold for about five seconds. And abruptly release feeling that tension fall away.

Pause for about 10 seconds.

Now smile widely, feeling your mouth and cheeks tense. Hold for about 5 seconds, and release, appreciating the softness in your face.

Pause for about 10 seconds.

Next, tighten your eye muscles by squinting your eyelids tightly shut. Hold for about 5 seconds, and release.

Pause for about 10 seconds.

Gently pull your head back as if to look at the ceiling. Hold for about 5 seconds, and release, feeling the tension melting away.

Pause for about 10 seconds.

Now feel the weight of your relaxed head and neck sink.

Breath in...and out.

In...and out.

Let go of all the stress

In...and out.

Now, tightly, but without straining, clench your fists and hold this position until I say stop. Hold for about 5 seconds, and release.

Pause for about 10 seconds.

Now, flex your biceps. Feel that buildup of tension. You may even visualize that muscle tightening.

Hold for about 5 seconds, and release, enjoying that feeling of limpness.

Breath in...and out.

Now tighten your triceps by extending your arms out and locking your elbows. Hold for about 5 seconds, and release.

Pause for about 10 seconds.

Now lift your shoulders up as if they could touch your ears. Hold for about 5 seconds, and quickly release, feeling their heaviness.

Pause for about 10 seconds.

Tense your upper back by pulling your shoulders back trying to make your shoulder blades touch. Hold for about 5 seconds, and release.

Pause for about 10 seconds.

Tighten your chest by taking a deep breath in, hold for about 5 seconds, and exhale, blowing out all the tension.

Now tighten the muscles in your stomach by sucking in. Hold for about 5 seconds, and release.

Pause for about 10 seconds.

Gently arch your lower back. Hold for about 5 seconds, relax.

Pause for about 10 seconds.

Feel the limpness in your upper body letting go of the tension and stress, hold for about 5 seconds, and relax.

Tighten your buttocks. Hold for about 5 seconds..., release, imagine your hips falling loose.

Pause for about 10 seconds.

Tighten your thighs by pressing your knees together, as if you were holding a coin between them. Hold for about 5 seconds...and release.

Pause for about 10 seconds.

Now flex your feet, pulling your toes towards you and feeling the tension in your calves. Hold for about 5 seconds, and relax, feel the weight of your legs sinking down.

Pause for about 10 seconds.

Curl your toes under tensing your feet. Hold for about 5 seconds, release.

Pause for about 10 seconds.

Now imagine a wave of relaxation slowly spreading through your body beginning at your head and going all the way down to your feet.

Feel the weight of your relaxed body.

Breathe in...and out...in...out....in...out

The Effects of Quartz Crystal Singing Bowl Music and Guided Relaxation on Mood and Sleep in Rangatahi (young adults)

What is this study about?

- An increasing number of rangatahi (young adults) report low mood and trouble sleeping but accessing help can be challenging.
- We want to find out if listening to music played on singing bowls or guided relaxation exercises improve mood and sleep

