Taken together these findings suggest that relaxation music played on singing bowls may be beneficial in improving mood, decreasing stress, and improving sleep. Extending the previous work by co-PI [name] [19], this study seeks to compare the effects of listening to quartz crystal singing bowl music with guided relaxation on mood, stress and sleep in a larger sample of young adults. Participants will be randomly assigned to either the singing bowl (SB) or guided progressive muscle relaxation (PMR) condition. Participants will be asked to listen to singing bowl music or complete the PMR exercises for 10 minutes three time a week for four weeks (delivered online via the Qualtrics platform) and will then be given free access to the music or guided meditation for another four weeks whilst their use is monitored. Ratings of mood, stress and sleep will be completed at baseline, 4 weeks and 8 weeks. For one session per week, participants will be asked to complete visual analogue rating scales of their mood/stress immediately before and after the session to determine the acute effects of the intervention.

3. Study Design and Method

a) Hypothesis

Listening to singing bowl music will result in equivalent improvements in mood, stress and sleep compared with guided relaxation immediately after the session, and at 4- and 8-weeks post-intervention.

b) Design

Randomised controlled trial.

c) Intervention

Singing bowl music (SB)

The singing bowl relaxation music ('Tranquility' available on Spotify) was played by [name] and professionally recorded. The sound is produced by tapping the bowls and rubbing them with a rubber mallet. Each session took approximately 10 minutes.

Guided relaxation (PMR)

A guided progressive muscle relaxation audio (recorded by the NZ Cancer Society <https://www.youtube.com/watch?v=Zydrp3rfJdY>) and similar to the PMR script from the Anxiety and Phobia Workbook by Edmund Bourne [20]) was used. The session took approximately 12 minutes. Participants were instructed to start by sitting or lying comfortably, taking some deep breaths and then tense and relax muscles in a sequential manner from the head to the feet (see Appendix 6 for an example of the PMR script).

d) Outcome measures

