Members of the general population aged 16-25 years will be recruited to participate in the study. To be eligible to take part, potential participants need to have good hearing, good understanding of English and have a mobile phone or computer to access the intervention and questionnaires via the Qualtrics application. Participants will be excluded if: they are regular users of relaxation music from quartz crystal singing bowls or progressive muscle relaxation, have an untreated mental health diagnosis, or are receiving treatment from a psychologist or psychiatrist. (See Appendix 1 for the eligibility questionnaire).

Participants will initially be recruited from the first-year psychology participant research pool (IPRP) and will receive up to 10% course credit for participation (as outlined in the flyer and participant information sheet (PIS) appendices 7 and 8. Study flyers will also be posted around the University to recruit more widely (participants can choose to enter a prize draw). In the next stage of the study, we will approach secondary schools to advertise the research to their students (subject to additional ethics approval).

We aim to recruit at least 100 participants, with a minimum of 50 university students.

5. Study Procedures

The study/questionnaires will be delivered via the Qualtrics software. Those interested in participating will contact the researchers via a study email address [contact]. Each participant will be allocated to one of the students who will be responsible for monitoring the participant's completion of the questionnaires and sending reminders to complete the intervention as needed. Participants will be sent an individual link to the information sheet, consent form, and eligibility form (Appendices 1, 8). Those meeting the eligibility criteria will automatically be directed to complete the demographic questionnaire (Appendix 2), and the mood (POMS) and sleep measures (modified Auckland Sleep questionnaire) Appendix 3 & 4, (T1).

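### The eligibility form asks about guided meditation and never names progressive muscle relaxation, so it does not reliably apply Section 4's exclusion of regular PMR users

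*Combined protocol and SAP*

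**What the plan says.** Section 4 (Study population) excludes people if "they are regular users of relaxation music from quartz crystal singing bowls or progressive muscle relaxation", and then directs the reader to the form: "See Appendix 1 for the eligibility questionnaire".

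Appendix 1 has two items on prior relaxation practice, each with No/Yes options. One is "Do you use singing bowls music regularly (more than once a month"; the other is "Do you use guided meditation regularly (more than once a month". PMR is not named in either, and no item describes tensing and relaxing muscles.

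Section 5 (Study Procedures) says how the form is used: "Those meeting the eligibility criteria will automatically be directed to complete the demographic questionnaire". No interview or second eligibility check is described.

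The introduction sets out the comparison: "Participants will be randomly assigned to either the singing bowl (SB) or guided progressive muscle relaxation (PMR) condition". Section 3c describes the comparator as an audio in which participants "tense and relax muscles in a sequential manner from the head to the feet". The introduction also says, of the second four weeks, that participants get "free access to the music or guided meditation for another four weeks"; there, guided meditation can only mean the PMR audio.

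**The concern.** The stated criterion has two halves, one for each intervention. The form carries out the first half directly and replaces the second with a differently named practice. Because entry is automatic, the wording of the item is in effect the criterion that gets applied.

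Two things are at stake. First, the enrolled population may differ from the one Section 4 describes, in both directions: some regular PMR users let in, some guided-meditation users possibly kept out. Second, the primary objective is equivalence of SB and PMR on Total Mood Disturbance at 4 and 8 weeks. Enrolees who already practise the comparator may respond differently to the PMR audio, or may practise PMR outside the study while allocated to SB. Either could blur the contrast. The plan would not show it: Appendix 2 does not record prior relaxation practice, use is monitored only through Qualtrics, and the only covariate the analysis plan mentions is the number of study sessions completed.

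**Working it through.** The plan gives no figure to reproduce here; the check is a comparison of texts, followed by a look at what can be said about size.

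**Criterion against form**

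| Section 4 excludes regular users of | Appendix 1 item | Match |
|---|---|---|
| Singing bowl music | Singing bowl music, more than once a month | Yes |
| PMR | None by that name or description | No |
| (guided meditation not listed) | Guided meditation, more than once a month | No such criterion |

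**Who is affected**

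- A regular PMR user who regards it as guided meditation answers Yes. The screen works.
- A regular PMR user who regards it as a muscle exercise answers No, truthfully, and proceeds to randomisation.
- A regular user of a mindfulness recording answers Yes. If Yes screens out, that person is refused although Section 4 does not exclude them. Appendix 1 shows no branching, so this step is inferred from the form's purpose.

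**How many**

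The documents give no prevalence of regular PMR use. For assumed shares of 2%, 5%, 10% and 20% of the 100 participants, the numbers would be 2, 5, 10 and 20. None of these shares is supported by the documents.

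**Effect on the contrast**

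Let p be the share of regular PMR users among enrolees. Randomisation makes p the same in both arms in expectation. Let δ_S and δ_P be the amounts by which their mean improvement differs from that of other participants in the SB and PMR arms. Each arm's mean improvement moves by p × δ for that arm, so the SB minus PMR difference moves by

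p × (δ_S − δ_P).

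- If regular PMR users improve less by the same amount in both arms, for example because they have less room to improve, δ_S = δ_P and the shift is zero.
- If their outside practice is constant and adds c to every score, the change from T1 is (y₂ + c) − (y₁ + c) = y₂ − y₁, and the practice cancels.
- A shift arises only if the two δ differ, for example because repeated PMR adds less for experienced users, or because outside practice changes after T1.

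The documents give neither δ, so the sign and size of the shift are undetermined.

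**An illustrative extreme**

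Suppose regular PMR users gain nothing from the PMR audio, other participants gain 0.5 SD (assumed), and δ_S = 0. The shift is then p × 0.5:

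- p = 0.05: 0.05 × 0.5 = 0.025 SD
- p = 0.15: 0.15 × 0.5 = 0.075 SD

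The standard error of the arm difference with 50 per arm is √(1/50 + 1/50) = 0.20 SD. The plan states no equivalence margin against which to judge such shifts.

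**The case against.** The strongest reply is that this is a labelling slip. The introduction itself uses guided meditation for the PMR audio, and the example script in Appendix 6 includes focused attention, breathing and visualisation, so people who use PMR recordings could well answer Yes. Those currently under a psychologist or psychiatrist are caught by another item. This stands in part: the item was probably meant to cover PMR, and it will catch some users. But respondents are given no such definition on the form. The flyer calls the comparator guided relaxation, the closing message in Appendix 4 calls it progressive muscle relaxation, and the introduction discusses meditation and mindfulness apart from the study interventions. The information sheet was not available for this check; if it names PMR, that would help, but the form would still not match Section 4.

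A reader might also infer more than the documents support:

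- **That the comparator half of the exclusion does nothing.** It is unreliable, not absent.
- **That baseline confounding results.** Randomisation balances prior practice in expectation.
- **That only the PMR arm loses improvement, or that the SB arm's change contains the comparator's effect.** Less room to improve could apply in both arms, and stable practice largely cancels in change from T1.
- **That the PMR arm's improvement shrinks by 5% or 15%.** This needs both an assumed prevalence and zero further gain. The form's threshold is more than once a month, while the trial asks for 3 × 4 = 12 sessions in four weeks. For someone practising twice a month that is roughly a sixfold increase, so zero gain is hard to defend.

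**Conclusion.** The mismatch between Section 4 and Appendix 1 is certain on the face of the documents. Following the plan as written applies a different criterion from the one stated, and a regular PMR user can be enrolled without answering untruthfully. The possible refusal of guided-meditation users depends on a Yes answer screening out, which is likely but not shown.

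The consequence for the primary comparison is possible blurring of the SB versus PMR contrast, of unknown size and direction. The calculations above are illustrations under assumed values, not estimates. This is a clear error in the screening instrument that is worth correcting; the documents do not show that it invalidates the comparison.

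**What to change.** Reconcile Section 4 and Appendix 1. Reword the Appendix 1 item so that it names and plainly describes PMR, for example: *Do you use progressive muscle relaxation (tensing and relaxing muscle groups in turn, guided or on your own) regularly (more than once a month)?* If guided-meditation users are also meant to be excluded, keep that item as a separate question and add the criterion to Section 4; if not, remove it.

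Optionally, ask anyone already enrolled about PMR use before the study and run a sensitivity analysis without regular users. Answers given after exposure to the PMR track are open to recall error, and with few such participants the analysis may show little.

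The cost is a minor form amendment and the loss of a few PMR users who would otherwise have entered. The optional step adds contact with participants and one further analysis.
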